5.5. Dose Modification

Dacomitinib will be available at 3 dose strengths, 45 mg, 30 mg, and 15 mg once daily.

Table 2 outlines dose modifications that will apply to patients order to manage treatment-related toxicity that is not controlled by optimal supportive care, or not tolerated due to symptomatology or interference with normal daily activities regardless of severity.

Table 2. Doses of Study Drug Administered

Dose level	Dacomitinib
Level 0	45 mg
Level -1	30 mg
Level -2	15 mg

Dose reductions may take place whenever toxicity that is not controlled with optimal supportive care is noted during the trial. If a patient subsequently tolerates therapy well in the judgment of the investigator, resumption of the next higher dose level may be undertaken. If a patient still cannot tolerate treatment after a dose reduction to the lowest dose of 15 mg, treatment will be discontinued. If a patient is responding to dacomitinib but is requiring a dose modification below 15 mg, the investigator must discuss the situation with the Sponsor's Medical Monitor.

For Grade 3, Grade 4, or intolerable Grade 2 toxicity, treatment will be interrupted. Upon recovery to Grade ≤ 2 or baseline, and per the clinical judgment of the investigator and agreement of the patient, the treatment will be resumed:

- For treatment interruption due to Grade 3 or intolerable Grade 2 toxicity, treatment may be resumed at the same or a lower dose level;
- For episodes of Grade 4 toxicity, reduction to the next lowest dose level is mandated.

If the patient fails to recover within 2 weeks of discontinuation, treatment will be discontinued unless there is discussion of the clinical circumstance with the Sponsor and agreement that the patient may resume treatment after a lapse of greater than 2 weeks. The patient will undergo end of treatment evaluations and follow-up visit as per [Schedule of Activities](#).

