5.6. Adverse Event Management

Specific guidance which has been developed for the management of common EGFR tyrosine kinase inhibitor toxicity at various grades is provided in [Appendix 1](#). In general (and not as substitute for consideration of the more specific guidance in [Appendix 1](#)):

For diarrhea, patients should begin therapy with loperamide at first evidence of increased frequency of bowel movement with adjustment in dose or prescription of alternative medication when necessary. The potential need for increased oral hydration (including electrolyte-containing fluids) should also be evaluated. There is a risk of pre-renal azotemia noted from poor fluid intake in the face of diarrhea and/or stomatitis. Monitor renal function tests and consider supplemental IV hydration if necessary.

For prevention of dry skin, patients should begin a regimen of moisturizers prior (ideal) or with start of dosing, and use appropriate measures to prevent excessive sun exposure.

Treatment of acneiform rash may include topical steroids, topical antibiotics, and oral antibiotics.

Mucositis can be treated with antibiotic-free oral rinse; chlorhexidine should be avoided.

Other measures may be utilized per the investigator judgment or emerging data-driven guidelines where these are available

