Grade 3: increase of ≥7 stools per day over baseline; or incontinence; or limiting self care ADL: or hospitalization indicated	
Oral therapy with diphenoxylate hydrochloride and atropine sulfate formula, or tincture of opium.
 
Fluid intake of at least 2 L should be maintained, intravenously if necessary.
 
Consider use of octreotide (Sandostatin[®]) 100-150 microgram (µg) subcutaneously twice daily with escalation to 500 µg three times daily.
 
Consider hospitalization if does not improve to Grade 2 within 24 hours, or in presence of fever, abdominal pain, etc.
 
Study Treatment: Hold therapy. Upon resolution to Grade ≤1, resume therapy with consideration of reduction of one dose level

Grade 4: life-threatening	
Maximal inpatient fluid and nutritional support, antibiotics as indicated in judgment of investigator for fever, leucocytosis, marked dehydration, etc.
 
Study Treatment: Hold until ≤ Grade 1. Mandatory dose reduction of one dose level

DERMATOLOGIC TOXICITY

Acneiform/ Papulopustular Rash:

	Acneiform/ Papulopustular Rash Management Guideline

Grade 1:
 
<10% body surface area (BSA) papules and/or pustules (with or without symptoms of pruritis or tenderness)
	
Topical steroids *
 
And
 
Topical antibiotic bid (clindamycin 1 - 2%, erythromycin 1% - 2%, metronidazole 1%)

Grade 2:
 
10 to 30% BSA papules and/or pustules (with or without symptoms of pruritis or tenderness), or psychosocial impact, or limited instrumental ADL
	
Oral antibiotic for at least 4 weeks (doxycycline 100 mg bd, minocycline 100 mg bd or oxytetracycline 500 mg bd);
 
Stop topical antibiotic if being used
 
And
 
Topical steroids *

Grade 3:
 
>30% BSA papules and / or pustules (with or without symptoms of pruritis or tenderness); or
 
 • limiting self-care ADL: or • associated with local superinfection with oral antibiotics indicated 	
Oral antibiotic for 4 weeks (doxycycline 100 mg bd, minocycline 100 mg bd or oxytetracycline 500 mg bd)
 
If infection suspected (yellow crusts, purulent discharge, painful skin/nares):
 
switch oral antibiotic to broad spectrum/gram negative cover for at least 10 days
 
consider skin swab for bacterial culture,
 
And
 
Topical steroids (continue)*
 
Consider dermatology consultation

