Grade 3: Limiting self-care ADL	Preservative free artificial tears, ointments, and/or other therapies as clinically indicated, with a follow-up examination within 2 weeks to include slit-lamp and fundoscopic exam as per the investigator judgment. Study Treatment: Drug should be withheld until recovers to \leq Grade 1 and then reduce one dose level.

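### After Grade 3 keratoconjunctivitis, Section 5.5 permits a same-dose restart that Appendix 1 excludes, and no text says which governs

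*Protocol*

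**What the plan says.** Protocol Section 5.5 (Dose Modification) interrupts treatment for Grade 3, Grade 4 or intolerable Grade 2 toxicity and sets a general condition for restarting: "Upon recovery to Grade ≤ 2 or baseline". Two bullets then fix the dose at restart. The first reads "For treatment interruption due to Grade 3 or intolerable Grade 2 toxicity, treatment may be resumed at the same or a lower dose level". The second is the only compulsory reduction in the section: "For episodes of Grade 4 toxicity, reduction to the next lowest dose level is mandated". Neither bullet is limited by type of event, and the section does not mention Appendix 1. Table 2 gives three levels: 45, 30 and 15 mg.

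Appendix 1 (Adverse Event Management Guidelines) has a keratoconjunctivitis table. Its Grade 3 row says "Drug should be withheld until recovers to" Grade 1 or lower, after which the dose comes down one level. Its Grade 2 row gives the same sequence once symptoms have lasted 2 weeks or more. Both rows contain the words "Grade 1 and then reduce one dose level".

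Section 5.6 (Adverse Event Management) introduces its own list of care advice with "In general (and not as substitute for consideration of the more specific guidance in" Appendix 1.

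**The concern.** The two places answer the same question, the dose at which a patient restarts after a severe eye toxicity, and one permits what the other rules out. An investigator reading only Section 5.5 could put the patient back on the dose at which the event occurred. An investigator reading the Appendix 1 row could not. A monitor checking adherence under Section 10 has no stated basis for deciding whether a same-dose restart is a deviation.

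The secondary objective is long-term safety and tolerability. Sections 9.3 and 9.4 summarise study drug administration and the frequency, severity and timing of adverse events. Restart dose, and any recurrence after it, feed those descriptive summaries and would depend partly on which page a site followed.

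**Working it through.** There is no planned figure to reproduce: enrolment is not predetermined and no inference is planned. The check is a comparison of texts, worked through the dose levels in Table 2.

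**Step 1: isolate the dose question.** The recovery thresholds also differ (Grade 2 or lower, or baseline, in Section 5.5; Grade 1 or lower in Appendix 1). To set that aside, take a patient whose Grade 3 keratoconjunctivitis has recovered to Grade 1. Both thresholds are met, and only the restart dose remains.

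**Step 2: apply each text to that patient.**

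| Dose at onset | Section 5.5 permits | Appendix 1 gives | Gap if the same dose is chosen |
|---|---|---|---|
| 45 mg | 45 mg or lower | 30 mg | 45 − 30 = 15 mg; 15/45 = 33% |
| 30 mg | 30 mg or lower | 15 mg | 30 − 15 = 15 mg; 15/30 = 50% |
| 15 mg | 15 mg | one level below 15 mg | no such level in Table 2 |

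In the first two rows the Appendix 1 dose lies within what Section 5.5 permits, so a one-level reduction meets both texts. The conflict is the same-dose option. In the third row Appendix 1 cannot be followed within Table 2. What remains is the general Section 5.5 text on discontinuing a patient who cannot tolerate 15 mg, or discussing a responding patient who needs less with the Medical Monitor.

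**Step 3: Grade 2.** The triggers differ: intolerability in Section 5.5, duration of 2 weeks or more in Appendix 1.

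- Intolerable and lasting 2 weeks or more: both texts apply, and the restart doses conflict as in Step 2.
- Intolerable but shorter: only the Section 5.5 bullet applies, so there is no conflict.
- Tolerable but lasting 2 weeks or more: Appendix 1 requires withholding and reduction. Section 5.5 requires no interruption, though it allows a reduction when toxicity is not controlled by supportive care. This is a mismatch over whether to hold treatment. Section 5.5 has no restart-dose rule for this patient.

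**Step 4: is the Appendix 1 reduction only a suggestion?** Where Appendix 1 leaves the reduction open, it says so. For Grade 3 diarrhea it reads "resume therapy with consideration of reduction of one dose level", which agrees with Section 5.5 on dose; its Grade 4 diarrhea row makes the reduction compulsory, as Section 5.5 does. The two keratoconjunctivitis rows carry no such softening.

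**Step 5: does any text set precedence?** The nearest is Section 5.6: "and not as substitute for consideration of the more specific guidance in" Appendix 1. That phrase qualifies the advice that follows it on diarrhea, dry skin, rash and mucositis. It does not mention the restart bullets of Section 5.5.

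**The case against.** The strongest reply is that a permissive general rule stands beside a narrower specific one, so the two are not incompatible commands. Section 5.5 says treatment may resume at the same or a lower dose. Section 5.6, which follows directly, presents Appendix 1 as specific guidance by grade. A careful investigator would apply the specific row within the latitude Section 5.5 gives, and at 45 mg and 30 mg that satisfies both.

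Most of this stands, and it rules out a stronger reading: that a site following either text necessarily deviates from the other. The documents do not support that, because a site that reduces one level under Appendix 1 also complies with Section 5.5. Only the same-dose restart is affected. The reply does not close the gap, because no text says Appendix 1 limits the choice that Section 5.5 grants, and the appendix is titled as guidelines. A site could reasonably treat Section 5.5 as the binding dose rule.

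It is also fair that the effect on results is modest. The endpoint is adverse events, all summaries are descriptive, and administered doses are recorded on the CRF (Section 5.4), so actual restart doses stay visible. Section 5.5 leaves resumption to investigator judgment and patient agreement and allows later re-escalation. Some variation is therefore intended, and a difference at restart need not last.

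**Conclusion.** The contradiction is real but narrow. Section 5.5 permits a same-dose restart after Grade 3 keratoconjunctivitis, and after Grade 2 that is both intolerable and lasts 2 weeks or more; Appendix 1 excludes it in both cases. Where the same-dose option is taken, the texts differ by 15 mg a day, which is 33% at 45 mg and 50% at 30 mg. At 15 mg, Appendix 1 points to a level that does not exist.

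A reader might infer that these differences affect every Grade 3 case and every persistent Grade 2 case. They do not: they arise only when the investigator chooses the same dose, and a persistent but tolerable Grade 2 event has no Section 5.5 restart dose to conflict with. The protocol gives no incidence for keratoconjunctivitis, so the number of patients affected cannot be estimated.

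The conclusion assumes that the unsoftened Appendix 1 wording is meant as an instruction and that Section 5.6 sets no precedence over Section 5.5. No inferential result is at risk. The point merits correction because it concerns a dosing instruction after severe toxicity and bears on the descriptive tolerability summaries.

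**What to change.** Reconcile the restart bullets in Section 5.5 with the Grade 2 and Grade 3 keratoconjunctivitis rows of Appendix 1 so that one restart-dose rule applies. State in Section 5.5 which text governs wherever Appendix 1 carries a study-treatment instruction. The same edit should make clear how the Appendix 1 rows apply to a patient already on 15 mg, and whether a persistent but tolerable Grade 2 event is to be interrupted. The sponsor's clinicians decide which rule stands.

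The cost is one or two sentences in a protocol amendment, with no added visits, data or patients.

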5.6. Adverse Event Management

Specific guidance which has been developed for the management of common EGFR tyrosine kinase inhibitor toxicity at various grades is provided in [Appendix 1](#). In general (and not as substitute for consideration of the more specific guidance in [Appendix 1](#)):

For diarrhea, patients should begin therapy with loperamide at first evidence of increased frequency of bowel movement with adjustment in dose or prescription of alternative medication when necessary. The potential need for increased oral hydration (including electrolyte-containing fluids) should also be evaluated. There is a risk of pre-renal azotemia noted from poor fluid intake in the face of diarrhea and/or stomatitis. Monitor renal function tests and consider supplemental IV hydration if necessary.

For prevention of dry skin, patients should begin a regimen of moisturizers prior (ideal) or with start of dosing, and use appropriate measures to prevent excessive sun exposure.

Treatment of acneiform rash may include topical steroids, topical antibiotics, and oral antibiotics.

Mucositis can be treated with antibiotic-free oral rinse; chlorhexidine should be avoided.

Other measures may be utilized per the investigator judgment or emerging data-driven guidelines where these are available

5.7. Drug Storage

The investigator, or an approved representative, eg, pharmacist, will ensure that all investigational products, including any comparative agents and/or marketed products are stored in a secured area with controlled access under recommended storage conditions and in accordance with applicable regulatory requirements.

Investigational product should be stored in its original container and in accordance with the drug label. See the Dosage and Administration Instructions (DAI) for storage conditions of the product.

Storage conditions stated in the SRSD will be superseded by the storage conditions stated in the labeling.

Site systems must be capable of measuring and documenting (for example, via a log), at a minimum, daily minimum and maximum temperatures for all site storage locations (as applicable, including frozen, refrigerated and/or room temperature products). This should be captured from the time of investigational product receipt throughout study. Even for continuous monitoring systems, a log or site procedure which ensures active daily evaluation for excursions should be available. The operation of the temperature monitoring device and storage unit (for example, refrigerator), as applicable, should be regularly inspected to ensure it is maintained in working order.

Any excursions from the product label storage conditions should be reported upon discovery. The site should actively pursue options for returning the product to labeled storage conditions, as soon as possible. Deviations from the storage requirements, including any actions taken, must be documented and reported to the Sponsor.

Once an excursion is identified, the investigational product must be quarantined and not used until the Sponsor provides documentation of permission to use the investigational product. Specific details regarding information the site should report for each excursion will be provided to the site.

Site staff will instruct patients on the storage requirements for take home medications including how to report temperature excursions.

The Investigational Product Manual should be referenced for any additional guidance on storage conditions and actions to be taken when conditions are outside the specified range.

5.8. Drug Accountability

The investigator's site must maintain adequate records documenting the receipt, use, loss, or other disposition of the drug supplies. The sponsor or designee will provide guidance on the destruction of unused investigational product (eg, at the site).

5.9. Concomitant Treatment(s)

Anticancer therapy with agents other than dacomitinib is not allowed.

5.9.1. CYP2D6 Substrates

The use of drugs that are highly dependent on CYP2D6 for metabolism requires consideration of both the therapeutic index and the degree of CYP2D6 metabolism. Substitution within the therapeutic class is recommended if possible, otherwise the directions below should be followed.

- Drugs dependent on CYP2D6 metabolism with narrow therapeutic index are prohibited: eg, procainamide, pimozide and thioridazine.
- Administration of drugs which are highly dependent on CYP2D6 metabolism: dose reduction should be based on substrate sensitivity to CYP2D6 metabolism. As a guidance, a starting dose reduction of 75% (25% of the dose given without co-administration with dacomitinib) and close clinical monitoring is required.
- For drugs that are partly dependent on CYP2D6-mediated metabolism, there is a high likelihood of supra-therapeutic exposure in combination with dacomitinib. No dose reduction is required when starting dacomitinib but clinical monitoring is required and, based on patient response, dose-reduction may be necessary.

- Pro-drugs, or drugs with highly active metabolites such as codeine and tramadol should be replaced by an alternative within the therapeutic class as conversion to the pharmacologically active moiety is CYP2D6 metabolism-dependent and their exposure with the co-administration of dacomitinib may be sub-therapeutic. Opiates such as morphine, hydromorphone, oxycodone and oxycodone can be used as substitutes to replace codeine or tramadol for analgesia.

[Appendix 2](#) provides a comprehensive list of CYP2D6 substrates coded according to the therapeutic index and the degree of CYP2D6 metabolism. This is not an all-inclusive list. If there is uncertainty whether a concomitant medication is contraindicated, the Investigator should contact the Sponsor study team.

5.9.2. P-glycoprotein

Concurrent administration of drugs which are P-glycoprotein (P-gp) substrates and have a narrow therapeutic index should be monitored for exaggerated effect and/or toxicities.

5.9.3. Strong Amines

Lidocaine exposures may significantly increase in the presence of strong amines, such as dacomitinib. Lidocaine may be used systemically but clinical monitoring (including telemetry) is recommended.

5.10. Supportive Care

Patients may receive ongoing supportive and palliative care (eg, pain control) as clinically indicated throughout the study.

Patients who are receiving bisphosphonates at study entry may continue bisphosphonates while on study. However, the initiation of bisphosphonate therapy after enrollment will be considered progression of disease unless otherwise agreed by the investigator in consultation with the Sponsor.

6. STUDY PROCEDURES

Informed Consent: All patients being considered for this study must sign an informed consent document prior to any study-related procedures that are not considered to be standard of care and prior to receiving study drug.

Registration: The site staff will fax/e-mail a complete Registration Form to the designated Sponsor study team member. The Sponsor will assign a patient identification number, which will be used on all CRF pages and other study-related documentation or correspondence referencing that patient and fax/e-mail to the site.

Assessments for screening and all other study time points are detailed in the [Table 1](#) (Schedule of Activities).

6.1. Patient Withdrawal

Patients may withdraw from the study at any time at their own request, or they may be withdrawn at any time at the discretion of the investigator or Sponsor for safety or behavioral reasons, or the inability of the patient to comply with the protocol-required schedule of study visits or procedures at a given study site. Reasons for withdrawal include, but are not limited to the following:

- Progressive disease;
- Unacceptable toxicity;
- Global deterioration of health-related symptoms;
- Study non-compliance;
- Pregnancy;
- Patient request;
- Lost to Follow-Up;
- Study termination by Sponsor.

If a patient requires more than 2 consecutive weeks of dosing interruption, a discussion should be held with the Sponsor to determine whether or not to withdraw the patient from the study.

If a patient does not return for a scheduled visit, every effort should be made to contact the patient. All attempts to contact the patient and information received during contact attempts must be documented in the patient's medical record. In any circumstance, every effort should be made to document patient outcome, if possible. The investigator should inquire about the reason for withdrawal, request the patient to return all unused investigational product(s), request the patient to return for a final visit, if applicable, and follow up with the patient regarding any unresolved adverse events.

If the patient withdraws from the study, and also withdraws consent for disclosure of future information, no further evaluations should be performed, and no additional data should be collected. The Sponsor may retain and continue to use any data collected before such withdrawal of consent.

7. ASSESSMENTS

Every effort should be made to ensure that the protocol-required tests and procedures are completed as described. However, it is anticipated that from time to time there may be circumstances, outside of the control of the investigator that may make it unfeasible to perform the test. In these cases the investigator will take all steps necessary to ensure the safety and well-being of the patient. When a protocol-required test cannot be performed, the

investigator will document the reason for this and any corrective and preventive actions that he or she has taken to ensure that normal processes are adhered to as soon as possible. The study team will be informed of these incidents in a timely fashion.

7.1. Pregnancy Testing

For female patient of childbearing potential, a serum or urine pregnancy test, with sensitivity of at least 25 mIU/mL, will be performed at screening, before investigational product administration at the baseline visit, and at the end of treatment visit. A negative pregnancy result is required before the patient may receive the investigational product. Pregnancy tests will also be done whenever 1 menstrual cycle is missed during the active treatment period (or when potential pregnancy is otherwise suspected), and at the end of the study to confirm the patient has not become pregnant during the study. Pregnancy tests may also be repeated as per request of institutional review boards (IRBs)/ethics committees (ECs) or if required by local regulations.

In the case of a positive confirmed pregnancy, the patient will be withdrawn from study medication and from the study.

